#### **Patients suffering from seizures**

- Patients with CVT often have seizures, requiring anticonvulsive treatment. Due to (a potential for) interactions with dabigatran etexilate and warfarin, phenytoin and carbamazepine should not be used in those cases. It is possible to use levetiracetam instead, if available.

### **4.2.2.2      Precautions regarding concomitant treatment**

#### **General precautions**

ASA, dipyridamole, clopidogrel, ticagrelor, prasugrel, corticosteroids, or non-steroidal anti-inflammatory drugs (NSAIDs) may be used if clinically indicated according to current treatment guidelines but it is strongly recommended to avoid these if possible. The patients should be advised to not use ASA-containing over-the-counter medications on a regular basis. In case of the need for pain relief, the use of acetaminophen, diclofenac or ibuprofen instead of ASA should be considered where appropriate. The use of these medications should be limited to the absolute minimum possible time period.

Co-administration of oral anti-platelet (including ASA) and NSAID therapies increase the risk of bleeding .

For any drug potentially increasing the risk of bleeding the factor age needs to be considered as the effect may be more pronounced in elderly patients ( $\geq 75$  years). If bleeding is clinically suspected, appropriate measures such as testing for occult blood in stool, or testing for a drop in haemoglobin is suggested . Investigators should assess the benefit-risk of the concomitant use of drugs that can promote bleeding, e.g., NSAIDs, corticosteroids and ASA, other anticoagulants and use them only when the benefits are thought to outweigh the risks.

### **Dabigatran Etexilate Treated Group**

The Investigator is alerted to the use of concomitant administration of moderate to strong P-gp inhibitors in patients receiving dabigatran etexilate (e.g. such as amiodarone, verapamil, quinidine, nelfinavir, ritonavir, saquinavir and tipranavir+ritonavir or lopinavir+ritonavir) or P-gp inducers due to a potential risk of higher or lower plasma levels of dabigatran and consequent exaggerated or reduced pharmacodynamic effect of dabigatran etexilate (notably bleeding or thromboembolic risk). Concomitant use of such drugs is not prohibited in this study *per se* (except for treatment with ketoconazole, itraconazole, posaconazole, cyclosporine, tacrolimus, dronedarone, rifampicin, phenytoin, carbamazepine or St. John's Wort), but should be used with caution or, at Investigator discretion, switched to a suitable alternative.

For patients in the RE-LY study who were concomitantly treated with verapamil, average dabigatran plasma concentrations increased by only 16% at trough and 20% two hours post-dose. Accordingly, the annualised bleeding rates in patients who had used verapamil at least once together with warfarin, dabigatran etexilate 110 mg b.i.d. or 150 mg b.i.d. were 3.33%, 3.09% and 3.92%, respectively. If verapamil is initiated during the course of this trial, it should be considered to separate the timing of administration of dabigatran etexilate and verapamil.

If dabigatran etexilate is given at least two hours before verapamil particularly in the first three days, the increase of dabigatran exposure will be reduced compared to taking verapamil and dabigatran etexilate at the same time-point.

In the RE-LY study, concomitant administration of amiodarone or quinidine and dabigatran etexilate did not increase the relative risk of bleeding compared to patients on warfarin and amiodarone or quinidine. As with verapamil separation of administration (dabigatran etexilate given at least two hours before any P-gp inhibitor) will mitigate any potential risk of drug interaction.

A list of common P-gp inhibitors will be provided in the ISF.

The concomitant use of dabigatran etexilate with the following treatments has not been studied and may increase the risk of bleeding: UFHs (except at doses necessary to maintain patency of central venous or arterial catheter) and heparin derivatives, LMWHs, fondaparinux, desirudin, ticlopidine, dextran, sulfapyrazone, prasugrel, direct thrombin inhibitors, VKAs.

Bleeding risk may be increased in patients concomitantly treated with selective serotonin re-uptake inhibitors or selective serotonin norepinephrine re-uptake inhibitors

### **Warfarin Treated Group**

Patients randomised to receive warfarin must be aware of the potential risk of over- or under dosing with changes of co-medications (e.g. use of antibiotics), including over the counter medicines, herbal remedies or vitamin preparations.

For more specific advice on potential interactions with warfarin and on how to handle those, please refer to the summary of product characteristics that will be provided in the ISF.

#### **4.2.2.3      Restrictions on diet and life style**

Dabigatran etexilate can be taken with or without food. There are no specific dietary restrictions with dabigatran etexilate, whereas patients randomised to warfarin need to follow dietary instructions regarding their vitamin K intake. They must also be aware of the potential risk of over- or under dosing with concomitant diseases (e.g. diarrhoea).

#### **4.2.2.4      Restrictions regarding women of childbearing potential**

WOCBP must be ready and able to use highly effective methods of birth control per International Conference on Harmonization M3(R2) [[R09-1400](#)] that result in a low failure rate of less than 1% per year when used consistently and correctly. This includes:

- Placement of intrauterine device (IUD) or intrauterine system (IUS; e.g. Mirena (IUS with low dose progesterone))
- Bilateral tubal occlusion
- Male sterilization (with the appropriate post-vasectomy documentation of the absence of sperm in the ejaculate)
- Complete sexual abstinence

Periodic abstinence, e.g. calendar, ovulation, symptothermal, post-ovulation methods, and withdrawal are not considered acceptable methods of contraception based on the above criterion of low failure rate of less than 1% per year.

Highly effective methods of contraception should be applied from signing of informed consent until the follow-up visit (Visit 6).

#### WOCBP are defined as:

Any female who has experienced menarche and does not meet the criteria for "women not of childbearing potential" as described below.

#### Women not of childbearing potential are defined as:

Women who are postmenopausal (12 months with no menses without an alternative medical cause) or who are permanently sterilized (e.g., hysterectomy, bilateral oophorectomy or bilateral salpingectomy).

Please also refer to the inclusion and exclusion criteria for this study (see Sections [3.3.2](#) and [3.3.3](#))

In the case of male patients participating in the trial, since there is no documented evidence to suggest a risk to sperm quality (for either dabigatran etexilate or warfarin), no special consideration is required.

#### **4.3 TREATMENT COMPLIANCE**

Principles regarding the evaluability of non-compliant patients will be outlined in the Trial Statistical Analysis Plan (TSAP). Decisions about evaluability of patients will be made at the Blinded Report Planning Meeting and at the latest prior to database lock.

##### **Patient randomised to receive dabigatran etexilate**

Based on capsule counts, treatment compliance will be calculated as the number of capsules taken, divided by the number of capsules which should have been taken according to the scheduled period, multiplied by 100.

Doses taken on the current visit day will be excluded from the count and doses taken on the previous visit day will be included in the count.

$$\text{Treatment compliance (\%)} = \frac{\text{Number of tablets actually taken} \times 100}{\text{Number of tablets which should have been taken}^2}$$

A patient will be considered as non-compliant if the number of doses taken is not between 80-120% of the expected number of doses. If compliance does not meet this range the patient should be asked to provide an explanation and be re-informed about the purpose and conduct of the trial. Non-compliance should be discussed with BI.

##### **Patient randomised to receive warfarin**

Warfarin compliance will be monitored by means of the INR rather than by pill counts as it is a more accurate and biologic measure of pharmacodynamic effect.

The quality of warfarin therapy for each patient will be assessed by reporting the number of INR values within the indicated therapeutic target range (2.0 – 3.0) as well as those above and below this range. The Rosendaal method [R08-1695] will be used to evaluate the percentage of time that a patient's INR is in range (i.e. time in therapeutic range (TTR)). For each calendar month, the mean of all INR values will be reported. This will be calculated for each patient, for each centre, for each country and for the whole study. The mean percentage of time of INR in range will be calculated for each centre and each country during the trial conduct to monitor the INR control. The percentage of time of INR in range for each country and for the trial will be reported at study end.

 Despite the trial being open label, medical and quality review will be performed without reference to the trial treatment that the patient receives.

 The number of tablets which should have been taken should take into account any temporary interruptions in trial medication

## **5. VARIABLES AND THEIR ASSESSMENT**

### **5.1 TRIAL ENDPOINTS**

#### **5.1.1 Primary Endpoint(s)**

The primary endpoint for this trial is the composite of the number of patients with major bleeding according to ISTH criteria and VTE (recurring CVT; DVT of any limb, PE, splanchnic vein thrombosis) after up to 24 weeks. All components are adjudicated in a blinded manner by an AC.

#### **5.1.2 Secondary Endpoint(s)**

All secondary endpoints will be based on adjudicated data (except for any bleeding event).

The secondary efficacy endpoints are:

- Number of patients with recurring CVT; DVT of any limb, PE or splanchnic vein thrombosis after up to 24 weeks
- Cerebral venous recanalisation as measured by the change in number of occluded cerebral veins and sinuses after up to 24 weeks

The secondary safety endpoints are:

- Number of patients with major bleeding according to ISTH criteria after up to 24 weeks
- Composite endpoint of number of patients with new ICH or worsening of the haemorrhagic component of a previous lesion after up to 24 weeks
- Number of patients with CRNMBe after up to 24 weeks
- Number of patients with major bleeding according to ISTH criteria or CRNMBe after up to 24 weeks
- Number of patients with any bleeding event after up to 24 weeks

#### **5.1.4 Classification of endpoints for trial disclosure purposes**

This trial and its results will be publicly disclosed. Disclosure of trial endpoints should include information as to whether or not the endpoint pertains to a known safety issue. For that purpose the primary endpoint (major bleeding according to ISTH criteria and VTE) and all secondary safety endpoints (major bleeding according to ISTH criteria, composite endpoint of new ICH or worsening of the haemorrhagic component of a previous lesion, CRNMBe, the composite of major bleeding according to ISTH criteria or CRNMBe, and the endpoint of any bleeding events) are considered to pertain to a known safety issue. The other endpoints are not.

### **5.2 ASSESSMENT OF EFFICACY**

#### **5.2.1 Venous thrombotic events**

VTE should meet the following criteria:

##### CVT

New neurological signs / symptoms or worsening of previous signs / symptoms with new CVT on neuroimaging.

New CVT must be confirmed by the AC by review of appropriate imaging as mentioned in Section [3.3.1](#) for the qualifying CVT.

##### DVT (of any limb)

DVT is generally documented by one of the following:

- Abnormal compression ultrasonography
- An intraluminal filling defect on venography
- At autopsy

Any suspected DVT must be confirmed by the AC by review of images and/or reports of venous compression ultrasonography or of venography.

##### Splanchnic vein thrombosis

The presence of endoluminal material or absence of flow in the extrahepatic portal veins or mesenteric veins as shown by duplex-Doppler ultrasound, or contrast-enhanced CT scan or MRI.

Any suspected splanchnic vein thrombosis must be confirmed by the AC by review of images and/or reports of above mentioned imaging techniques.

##### PE

Pulmonary embolism is generally documented by one of the following:

- An intraluminal filling defect in segmental or more proximal branches on spiral CT scan

Proprietary confidential information © 2017 Boehringer Ingelheim International GmbH or one or more of its affiliated companies

- An intraluminal filling defect or an extension of an existing defect or a sudden cut-off of vessels more than 2.5 mm in diameter on the pulmonary angiogram
- Perfusion defect of at least 75% of a segment with a local normal ventilation result (high-probability) on ventilation/perfusion lung scan
- Inconclusive spiral CT, pulmonary angiography or lung scintigraphy with demonstration of DVT in the lower extremities by compression ultrasonography or venography
- At autopsy

Any suspected PE must be confirmed by the AC by review of images and/or reports of any of the above in order to be considered a PE.

These events will be assessed based on clinical information and supporting imaging. No specific imaging will be required to be performed, but events will only be considered as confirmed if images as indicated above (from routine medical practice) that support the diagnosis are available.

Note: the endpoint of new VTE does NOT include retinal thrombosis

## **5.2.6 Cerebral venous recanalisation**

Cerebral venous recanalisation will be assessed by imaging and will be adjudicated by the AC. Due to the specific skills that are required to assess recanalisation, an investigator assessment of this endpoint will not be requested.

Recanalisation as a secondary efficacy endpoint will be assessed as described below, analogues to the calculations made by Miranda et al [[R16-2716](#)].

1. At baseline and at the end of treatment, occlusion of cerebral veins and sinuses will be scored as follows:

1 = full occlusion

0 = no occlusion or partial occlusion

2. This score will be applied to each of the veins and sinuses using the below conventions:

- Superior sagittal sinus, straight sinus, cavernous sinus, left jugular vein, right jugular vein will each be scored individually (i.e. each will be scored as either 0 or 1)

Proprietary confidential information © 2017 Boehringer Ingelheim International GmbH or one or more of its affiliated companies

- Right lateral transverse and sigmoid sinus will be scored together (i.e. 0 points if neither is fully occluded; 1 point if at least one of them is fully occluded)
- Left lateral transverse and sigmoid sinus will be scored together (i.e. 0 points if neither is fully occluded; 1 point if at least one of them is fully occluded)
- Superior petrous sinus and inferior petrous sinus will be scored together (i.e. 0 points if neither is fully occluded; 1 point if at least one of them is fully occluded)
- Deep venous system will be scored as system, irrespective of the number of occluded veins (i.e. 0 points if none is fully occluded; 1 point if at least one is fully occluded)
- Superficial cortical veins will be scored as system, irrespective of the number of occluded veins (i.e. 0 points if none is fully occluded; 1 point if at least one is fully occluded)
- Cerebellar veins will be scored as system, irrespective of the number of occluded veins (i.e. 0 points if none is fully occluded; 1 point if at least one is fully occluded)

3. For each individual patient a total score will be calculated at baseline and at the end of treatment.
4. A recanalisation score will subsequently be calculated for each patient as the difference between the baseline total score and the end of treatment total score.

Patients who died during the trial before an EOT scan is made and patients for whom for other reasons no EOT scan is available or analyzable will not be included in the analysis of recanalisation (this applies to change in number of occluded cerebral veins and sinuses)

Diagnosis of CVT and assessment of venous occlusion is expected to be performed by any of the following techniques or a combination of them:

- MRI + MR venography
- CT + CT venography
- MRI or CT in combination with angiography (DSA)

Patients are diagnosed prior to trial entry. The imaging that was performed for diagnosis of CVT (as part of the clinical routine) will be used as baseline assessment.

At EOT the assessment of recanalisation must be done by MRI+MR venography. These techniques are expected to provide a better view of any remaining venous occlusion than CT would. Furthermore, for WOCBP it is desirable to refrain from CT scans in the non-acute setting due to radiation exposure of CT scans.

A separate MRI protocol will be provided as part of the ISF and should be followed for the EOT imaging.

All scans (both baseline and EOT) will be sent in for central review by the AC. Review criteria will be outlined in the AC charter governing the adjudication process. Details on how to provide the images will be provided in the ISF. Central review will focus on assessment of endpoints (grade of cerebral venous recanalisation / recurrence of CVT).

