- 3) End of Treatment (EOT) and follow-up procedures (Visits 5 and 6) are performed for all patients at the time of discontinuation of trial medication. This includes patients who discontinue trial medication prior to Day 169 (the Day number does not apply in that case). See also footnotes 4 and 15.
- 4) Extended follow-up applies only to patients who discontinue trial medication early (see Section [3.3.4](#)).
- 5) Re-consenting may become necessary when new relevant information becomes available and should be conducted according to the sponsor's (Boehringer Ingelheim's) instructions.
- 6) National Institutes of Health Stroke Scale (NIHSS) is a tool used to evaluate impairment after a stroke. See Section [5.6.2](#). This neurological assessment is to be completed for the qualifying CVT.
- 7) Height is measured at screening only.
- 8) Pregnancy tests required for all women of childbearing potential. See Section [3.3.2](#) for definition of women of childbearing potential. A urine test is acceptable, unless local regulations demand a serum test to be performed. If a pregnancy test is not routinely performed in female CVT patients, the test at the Screening visit should be performed after informed consent has been obtained.  
In addition to the tests performed at the visits, women of child bearing potential will be supplied with pregnancy tests and instructed to perform pregnancy testing every 4 weeks when visits are more than 4 weeks apart.
- 9) At screening imaging should not be performed specifically for the trial. The imaging that was done for diagnosis of the cerebral venous or dural sinus thrombosis (CVT) will be used and should be submitted for review by the trial's Adjudication Committee (AC). It is expected that CVT is diagnosed and venous occlusion assessed by any of the following techniques: MRI+MR venography, CT+CT venography or MRI or CT in combination with catheter angiography (DSA).
- 10) At EOT the assessment of recanalisation must be done by MRI+MR venography. A separate MRI protocol will be provided as part of the ISF and should be followed for the EOT imaging. The EOT images should be submitted for review by the Adjudication Committee.
- 11) Throughout the trial, whenever routine imaging is performed due to worsening of the patient's condition, a suspected new intracranial haemorrhage or a new venous thrombotic event (VTE), those images are to be made available to the trial's AC for independent blinded review.  

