EOT assessment of intracranial haemorrhage is to be done by MRI (see also Footnote 10).
- 12) Assessment of International Normalised Ratio (INR) for:
  - Patients who are on a vitamin K antagonist (VKA) prior to randomisation. At least one measurement prior to start of trial treatment in order to determine when to stop initial parenteral therapy and when to start trial treatment (see Section [4.1.4](#)); further measurements until start of trial treatment as outlined in Section 4.1.4;
  - Patients randomised to warfarin. Daily measurements from just prior to start of treatment until concomitant heparin treatment is stopped. At least two-weekly INR measurements for the first three months and monthly subsequently.
- 13) At Visit 2 information on any new venous thrombotic events since signing of consent is collected.
  
- 15) Completion of patient participation
  - Patients who complete the full treatment period of 169 days complete their participation at the follow-up visit (Visit 6);
  - Patients who discontinue trial medication early (see Section 3.3.4): after the follow-up visit they should be followed , for major bleeding events, VTE events and any other adverse events until Day 176 (25 weeks) after randomisation. They complete participation at that moment.

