In patients with CVT, 30-40% present with intracerebral haemorrhage [[R15-5859](#), [R15-5863](#)]. The haemorrhage in CVT is believed to be caused by venous outflow blockage and very high intradural and intravenous pressure, leading to both rupture of venules and to haemorrhagic transformation of venous infarctions. This difference in aetiology compared to arterial haemorrhagic stroke is why anticoagulation is not contraindicated in this setting.

Clinical trial results support this approach, as reflected in the AHA/ASA guidelines [[R15-5005](#)].

Magnetic resonance imaging (MRI) in combination with magnetic resonance (MR) venography is the most sensitive examination technique for demonstrating the thrombus and the occluded dural sinus or vein (absence of flow and intraluminal venous thrombus). Computed tomography (CT) venography is a useful alternative to MR venography. Although a head CT scan alone is normal in up to 30 percent of CVT cases and most of the findings with CVT are nonspecific; the overall accuracy of head CT combined with CT venography is 90 to 100 percent. Cerebral intra-arterial angiography is recommended when the diagnosis of CVT is uncertain, such as in the rare suspected cases of isolated cortical vein thrombosis, or when the clinical suspicion for CVT is high but CT venography or MR venography are inconclusive [[R15-5005](#)]. Regarding relevant lab values, an elevated plasma D-dimer level supports the diagnosis of CVT, but a normal D-dimer does not exclude CVT in patients with suggestive symptoms *and predisposing factors* [[R15-5005](#)]. In contrast, a recent meta-analysis concluded that *in low-risk patients* with isolated headache the absence of increased D-dimer levels does have a high predictive value for excluding CVT. In these patients D-dimer is as sensitive for diagnosing CVT as it is in Pulmonary Embolism (PE) and deep venous thrombosis (DVT) [[R15-6315](#)].

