### **5.3.5      Other safety parameters (safety endpoints)**

#### **5.3.5.1      Composite endpoint of new haemorrhagic brain lesion or worsening of the haemorrhagic component of a previous lesion**

The neuroimaging which established the diagnosis of CVT will be used as baseline value. The safety endpoint "new haemorrhagic brain lesion or worsening of the haemorrhagic component of a previous lesion" will be assessed by comparing repeated neuroimaging that is routinely performed if the patient has a neurological worsening during the trial, or at the EOT visit, to the baseline image. The comparing of images and the categorisation of the lesions (see below) will be done by the AC.

A separate MRI protocol will be provided as part of the ISF and should be followed for the EOT imaging.

In order to assess any worsening of previous lesions, haemorrhagic brain lesions at baseline and during treatment / at EOT will be categorised as indicated in Table [5.3.5.1: 1](#) below, according the definitions as recommended by Von Kummer et al [[P15-09432](#)]:

Table 5.3.5.1: 1      Categorisation of haemorrhagic brain lesions

Class	Type	Description
1		Haemorrhagic transformation of infarcted brain tissue
1a	HI-1*	Scattered small petechiae, no mass effect
1b	HI-2	Confluent petechiae, no mass effect
1c	PH-1*	Haematoma within infarcted tissue, occupying <30%, no substantive mass effect
2		Intracerebral haemorrhage within and beyond infarcted brain tissue
	PH-2	Haematoma occupying 30% or more of the infarcted tissue, with obvious mass effect
3		Intracerebral haemorrhage outside the infarcted brain tissue or intracranial-extracerebral haemorrhage
3a		Parenchymal haematoma remote from infarcted brain tissue
3b		Intraventricular haemorrhage
3c		Subarachnoid haemorrhage
3d		Subdural haemorrhage

\* HI: haemorrhagic infarction; PH: parenchymatous haematoma

Any new haemorrhagic brain lesion will be categorised as Class 3 (Intracerebral haemorrhage outside the infarcted brain tissue or intracranial-extracerebral haemorrhage).

If there is more than one haemorrhagic lesion present on imaging, the category of the most severe lesion is assigned.

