7.5 SECONDARY ENDPOINT(S)

7.5.1 Key secondary endpoint(s)

This section is not applicable as no key secondary endpoint has been specified in the protocol.

7.5.2 (Other) Secondary endpoint(s)

The analyses for the secondary endpoints as described in Section 5.2.2 will be mainly based on frequency counts and percentages along with 95% CIs.

Means and standard deviations will be displayed for the endpoint on cerebral venous recanalisation as measured by the change in number of occluded cerebral veins and sinuses after up to 24 weeks. Patients with missing or not analyzable MRI scans at EOT will be excluded from this analysis.

The frequency of patients with new intracranial haemorrhage ("ICH") or worsening of the haemorrhagic component of a previous lesion will be presented, along with 95% CIs. The single components of this composite endpoint will be presented in the same way.

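### Both imaging change endpoints compare a baseline scan of any permitted modality with an MR scan at end of treatment, and the analysis does not separate true change from a change of instrument

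*Protocol*

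**What the plan says.** **Baseline, occlusion.** Protocol 5.2.6: "The imaging that was performed for diagnosis of CVT (as part of the clinical routine) will be used as baseline assessment". Footnote 9 of the Flow Chart rules out a dedicated scan: "At screening imaging should not be performed specifically for the trial". On technique, 5.2.6 says: "Diagnosis of CVT and assessment of venous occlusion is expected to be performed by any of the following techniques or a combination of them". It then lists MRI with MR venography, CT with CT venography, and MRI or CT with catheter angiography. Section 3.3.1 marks the first as preferred, not required.

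**EOT, occlusion.** Section 5.2.6 and footnote 10 make MRI with MR venography mandatory, under a separate MRI protocol. The reason given is "These techniques are expected to provide a better view of any remaining venous occlusion than CT would". In the same vein, Section 1.1 says that MRI with MR venography "is the most sensitive examination technique for demonstrating the thrombus and the occluded dural sinus or vein".

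**Haemorrhage.** Protocol 5.3.5.1 takes the diagnostic neuroimaging as the reference. Footnote 11 adds: "EOT assessment of intracranial haemorrhage is to be done by MRI". Section 5.3.5.1 also says: "Any new haemorrhagic brain lesion will be categorised as Class 3". SAP 5.2.2 defines worsening within Class 3 as a volume increase of at least 25%.

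**Analysis.** The recanalisation score is the baseline total minus the EOT total. SAP 7.5.2: "Means and standard deviations will be displayed for the endpoint on cerebral venous recanalisation". New or worse haemorrhage is shown as frequencies with 95% confidence intervals. Protocol 7.3.2 adds a summary of recanalisation by intracranial haemorrhage (ICH) at baseline and a Cochran-Mantel-Haenszel test for the ordinal haemorrhage classes. The sensitivity analysis in Protocol 7.5 concerns missing or unreadable EOT scans. Randomisation is stratified by ICH only (Protocol 7.6). Baseline modality appears nowhere in the visible analysis text.

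**The concern.** A change score is interpretable when the same thing is measured in the same way twice. Here the protocol says that its EOT instrument sees remaining occlusion better than one of the permitted baseline instruments, and then subtracts one reading from the other. The trial asks for more consistency in blood pressure, where Protocol 5.3.2 wants the same type of device throughout for each patient.

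For haemorrhage, a lesion that appears on the EOT scan but not on the baseline scan counts as new and goes into Class 3. The 25% volume rule has no condition that the two volumes come from the same modality.

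The trial tests no hypothesis (Protocol 7.2), so what it delivers on these endpoints is each arm's descriptive result. Randomisation does not protect a within-arm mean or percentage from a change of instrument. As planned, a reader of the report could not tell how much of the reported change comes from patients whose modality changed.

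**Working it through.** **Plan's own figure.** Protocol 7.7: 120 randomised, 10% drop-out. 120 × 0.90 = 108 and 60 × 0.90 = 54 per arm. This reproduces, and 54 is used below.

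**Scale of the score.** Protocol 5.2.6 and SAP 5.2.2 score five structures singly (superior sagittal, straight and cavernous sinus, left and right jugular vein). Six groups each get one point (right and left lateral/sigmoid, petrous, deep, superficial cortical, cerebellar). 5 + 6 = 11 items, each 1 for full occlusion and 0 for partial or none.

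**How the instrument enters one item, with no true change:**
- Fully occluded at both times, missed on a non-MR baseline, seen on EOT MR: 0 − 1 = −1.
- Partially occluded at both times, read as full on a non-MR baseline, residual flow shown on EOT MR: 1 − 0 = +1.

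Both are possible because only full occlusion scores. The sign is therefore open.

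**Size for recanalisation.** The documents do not give two inputs, so these are assumptions:
- f, the share of patients without MRI plus MR venography at baseline: 10%, 30% or 50%.
- s, the mean shift in such patients, in absolute size: 0.25, 0.5 or 1.0 point.

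Within-arm shift of the mean = f × s. The between-arm artefact has expectation 0, because the baseline scan precedes randomisation. Taking s as constant among the affected patients, its chance variation has SD = s × √(2f(1−f)/54), and the 95% range is ±1.96 × SD.

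| f | s | within-arm shift (absolute) | between-arm, 95% chance range |
|---|---|---|---|
| 0.1 | 0.25 | 0.025 | ±0.028 |
| 0.1 | 1.0 | 0.10 | ±0.113 |
| 0.3 | 0.5 | 0.15 | ±0.086 |
| 0.5 | 0.25 | 0.125 | ±0.047 |
| 0.5 | 1.0 | 0.50 | ±0.189 |

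Example, last row: 0.5 × 1.0 = 0.50; √(2 × 0.5 × 0.5/54) = 0.0962; 1.96 × 0.0962 × 1.0 = 0.189.

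The non-MR share itself can differ between arms by chance by ±11.3, ±17.3 and ±18.9 percentage points at f = 10%, 30% and 50%.

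**Haemorrhage.** No count is computed. The documents establish that the instrument changes, but say nothing on whether CT or MRI detects more haemorrhage or gives larger volumes. The follow-up scan may also be something other than MRI. Protocol 5.3.5.1 uses routine scans done for neurological worsening, and SAP 5.2.2 falls back on the last on-treatment images if there is no EOT visit.

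**The case against.** The strongest reply is that the affected group may be small and the consequence modest. MRI with MR venography is the preferred diagnostic technique. Section 1.1 puts the overall accuracy of CT with CT venography at 90 to 100 percent, although that figure is for the diagnosis and not for each sinus. The adjudication committee reads all scans centrally and blinded, under a charter that is not among the documents and may contain a rule for mixed modalities. The result offered to clinicians in Protocol 2.1 and 7.7 is the primary endpoint. An asymptomatic lesion found only on the EOT MRI does not meet the intracranial criterion for major bleeding in 5.3.5.2, which requires symptoms. All of this stands, and it limits the importance of the point. It does not remove it: a charter rule cannot make a baseline scan show what it does not show, and the visible SAP never separates the modality pairs.

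A reader might infer four stronger things that the documents do not support:
- *Recanalisation is understated, so the absolute rates are wrong.* Not shown. The sign is open, and the share and size are not given.
- *New ICH is overstated.* The statements on a better view and on sensitivity concern venous occlusion and thrombus, not haemorrhage.
- *A modality imbalance would look like a drug effect.* The expected artefact is zero, and chance imbalance is ordinary variability that the interval already carries. With an assumed score SD of 1 to 1.5 (none is given), the 95% half-width of a difference is 1.96 × √(2/54) × SD = 0.38 to 0.57, against at most ±0.19 above. No between-arm recanalisation model is planned either, so covariate adjustment has nothing to attach to.
- *The committee should excuse lesions that predate randomisation when the baseline was CT.* That would define a safety endpoint differently for CT and MRI patients, and it could only remove events.

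**Conclusion.** The point holds as a limited one. In patients without an MR baseline, the recanalisation score and the new-or-worse haemorrhage classification mix true change with a change of instrument, and the visible analysis pools them with everyone else. Under the assumed 10-50% share and 0.25-1.0 point shift, each arm's mean recanalisation moves by 0.025 to 0.50 point in an unknown direction. The between-arm artefact is zero in expectation, with a 95% chance range from ±0.03 to ±0.19. For haemorrhage the documents support the mismatch but no direction or size.

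What is at stake is the within-arm description of two secondary endpoints in an exploratory trial. The primary endpoint is not built on this baseline-to-EOT comparison. The change is worth making because it is cheap and uses scans already collected and read.

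**What to change.** In SAP 7.5.2:
1. Record the modality of the baseline scan that the adjudication committee reads, for each patient and endpoint.
2. Tabulate recanalisation and new or worse haemorrhage by baseline modality (MR versus non-MR) within each arm.
3. Prespecify a sensitivity analysis restricted to patients with MR imaging at both times: MRI with MR venography for recanalisation, MRI for haemorrhage. Define the subset separately for each endpoint, because a baseline of MRI with catheter angiography qualifies for the second but not the first.

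The same edit should confirm that the diagnostic scan is the imaging baseline. The general rule in SAP 6.7 takes the last measurement before first dose, which could point to a different scan.

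The cost is one extra table and a smaller subset with a wider interval. No imaging, visits, readers or patients are added, and the endpoint definitions stay as they are.
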